For the control group, the same investigational product will be administered, however the procedure for use will be modified as follows: There will be no mouth cleaning before the product consumption (No step 1 as mentioned above). The product will be swallowed instead of dissolved in the mouth, in order to reduce its presence in the mouth as much as possible. The purpose of this control group is to support the effect of use of the entire two-step method as compared to the investigational group.

The active ingredient, L-Arginine is known to Health Canada. L-Arginine is listed in the NHPID, and allowed for use in NHPs under proposed here conditions of use. Safety of the of current ingredient combination, while allowed for use separately, will also be tested under proposed conditions of use.

The Rationale for Performing Research:

Increase in immune-mediated conditions [30]–[32](Allergic rhinitis is one of them) and the few medical solutions available (each of which is associated with side effects) prompted this research and clinical study. The medicinal ingredient, L-Arginine, in the formulation of AllerPops is a well-known Natural Health Product Ingredient with history of human use.

4. Study Objectives

Objectives:

Primary Objective: To assess the effectiveness of AllerPops on relieving nasal symptoms compared to the control group in volunteers with seasonal and perennial (or intermittent and persistent) allergic rhinitis during the first 7 days of the 21-day intervention period.

Secondary Objectives:

1. To evaluate the safety of AllerPops administration in volunteers with seasonal/year-long allergies during a 21-day intervention period.
2. To assess the duration of effectiveness of AllerPops in relieving nasal symptoms compared to the control group in volunteers with seasonal/year-long allergies during a 21-day intervention period (exploratory).

3. To evaluate the effect of the AllerPops administration on the oral microbial presentation/microbiota using Amplicon Metagenomics Sequencing test through saliva samples during a 21-day intervention period (exploratory).
4. To evaluate the effect of the AllerPops administration on the IgE (total) blood level during a 21-day intervention period (exploratory).

Endpoints:

Primary Endpoint: The reduction of nasal allergic symptoms during the first 7 days of the 21-day intervention period (once every other day – D1, D3, D5). The reduction of symptoms will be measured using the following assessments.

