- Total Nasal Symptoms Score (TNSS) Questionnaire: This assessment will be conducted at the V1, V2, and V3.
- Peak Nasal Inspiratory Flow (PNIF): Measures nasal flow for assessing nasal airway patency. This assessment will be conducted at the baseline D1 and D7.

Secondary Endpoint(s):

1. To evaluate the safety of the AllerPops product during a 21-day intervention period. The safety evaluation will be measured based on the following assessments:
 - a. Safety will be assessed by collecting vital signs, the emergence of adverse events, and clinical chemistry (CBC and a comprehensive safety panel) and PI assessment.
2. The exploratory study of the effect of AllerPops in relieving nasal symptoms compared to the control group during a 21-day intervention period. The reduction of symptoms will be measured based on the following assessments:
 - a. Total Nasal Symptoms Score (TNSS) questionnaire: This will be assessed at D14 (V4) and D21 (V5).
 - b. Peak Nasal Inspiratory Flow (PNIF) measurement: This will be assessed at D14 and D21.
3. The exploratory study of the effect of AllerPops in oral microbial presentation/microbiota through Amplicon Metagenomics Sequencing test which is a rRNA gene sequencing method in saliva. The evaluation will be measured at D1, D7 and D21.
4. The exploratory study of the effect of AllerPops on the IgE (total) blood level through blood samples during a 21-day intervention period. The evaluation will be measured at D1, D7 and D21.

5. Selection of Study Population

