After informed consent has been obtained, the PI and/or delegated research site staff will collect demographic information, complete a thorough medical history which will include the review of existing medical records to confirm inclusion/exclusion criteria. Biometric measurements (body temperature, SSH blood pressure, heart rate), anthropometric measurements (height, weight, calculated BMI) will be taken and a short questionnaire to assess allergy symptoms will be conducted. If none of the collected information excludes participation, screening clinical chemistry assessments will be conducted.

The screening information will be reviewed by the PI and/or delegate to determine if the participant is to be scheduled for a physical examination* and a final eligibility assessment.

*Physical exam will be done before dosing. This may be scheduled on another day.

Participants that have met all of the inclusion criteria and none of the exclusion criteria will proceed to the next scheduled visit, and TNSS questionnaire will be administered.

For females of childbearing potential, a urine sample will be collected for a urine pregnancy test.

Blood samples to be collected will be analyzed for the following:

- CBC [Includes: White Blood Cell Count (WBC), Red Blood Cell Count (RBC), Hemoglobin (HB), Hematocrit (HCT), MCV, MCH, MCHC, Platelet Count]
- Aspartate aminotransferase (AST)
- Sodium
- Potassium
- Chloride
- Serum creatinine
- Alanine Amino Transferase (ALT)
- Alkaline Phosphatase (ALP)
- Bilirubin Total
- Gamma Glutamyl Transpeptidase (GGT)

Visit 2 – Baseline – Day 1

These assessments may not be completed in the order shown below.

Participants:

1. Must be at least 8 hours fasting (no food, only water) prior to visit.
2. Will have any changes to health reviewed by delegated study staff.
3. For females of childbearing potential, a urine sample will be collected for a urine pregnancy test.
4. Will have the following measurements taken: temperature, blood pressure, heart rate.

5. Will have the following saliva test:
 - Amplicon Metagenomics Sequencing
6. Will complete the following assessments:
 - Total nasal symptoms score (TNSS) questionnaire (appendix 2).
 - Peak nasal inspiratory flow (PNIF) measurement.
7. Will have the following blood tests:
 - CBC (WBC, RBC, Hb, HCT, MCV, MCH, MCHC, Platelet Count)
 - Aspartate aminotransferase (AST)
 - Alanine aminotransferase (ALT)
 - Bilirubin
 - Gamma-glutamyl transferase (GGT)
 - Alkaline phosphatase (ALP)

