11.1. Determination of Sample Size

Seventy-two participants will be participating in the study. The sample size was chosen based on the G*Power calculator in order to detect an effect of 0.6 (Medium effect size) considering 80% power in t tests. Parametric statistical techniques including, but not limited to t tests -

Means: Difference between two independent means (two groups) will be performed on data sets which meet all requirements for normality and variance. The application of non-parametric techniques might be used for relevant data sets. Should any of the statistical methods proposed prove unsuitable during the final analysis, more appropriate methods will be used, and any changes will be documented in the clinical study report, including the rationale for use. These include the transformation of the data (for example to a logarithmic scale) in order to satisfy model assumptions, if applicable. A p-value of < 0.05 will indicate statistical significance for all tests. An exploratory data analysis (EDA) will be performed for the exploratory study part to analyze and investigate data sets and summarize the main characteristics, employing data visualization methods.

[figure not shown]

Figure 1: Analysis: A priori: Compute required sample size.

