11.3. Analysis Plan

11.3.1. Primary Variables

- The Total Nasal Symptoms Score (TNSS) change from the screening (V1), baseline by comparing D1(V2) and D7(V3) for each group and the differences between groups (investigational and control) will be statistically assessed.
- Peak Nasal Inspiratory Flow (PNIF) values change from the baseline by comparing D1 and D7 for each group and the differences between groups (investigational and control) will be statistically assessed.

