11.3.3. Data Analysis

A descriptive statistics study will be performed for the primary variables. Continuous variables will be presented with the average and standard deviation or median range, as appropriate, and categorical variables will be presented as proportions. Parametric or non-parametric independent or related samples tests will be used, according to whether the distribution of the data in each variable is normal or not. A p-value < 0.05 is considered statistically significant. An EDA will be performed for the secondary variables (except safety) to analyze and investigate data sets and summarize their main characteristics, employing data visualization methods.

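### TNSS and PNIF are both primary and each is tested at p<0.05, but no rule says whether one or both must succeed: error is about 7 to 10% if either counts, and power is usually below 80% if both must

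*Combined protocol and SAP*

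**What the plan says.** Section 4 (Endpoints) names one primary endpoint, the reduction of nasal allergic symptoms over the first 7 days, and then gives two ways of measuring it: "The reduction of symptoms will be measured using the following assessments". These are the TNSS questionnaire and PNIF; of PNIF it says "This assessment will be conducted at the baseline D1 and D7".

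Section 11.3.1 (Primary Variables) treats them as two variables with parallel analyses. TNSS change is assessed "by comparing D1(V2) and D7(V3) for each group and the differences between groups (investigational and control) will be statistically assessed". The second item reads "Peak Nasal Inspiratory Flow (PNIF) values change from the baseline by comparing D1 and D7 for each group and the differences between groups", again to be statistically assessed.

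On significance, section 11.1 says "A p-value of < 0.05 will indicate statistical significance for all tests", and section 11.3.3 repeats "A p-value < 0.05 is considered statistically significant". The sample size of 72 in section 11.1 was chosen "to detect an effect of 0.6 (Medium effect size) considering 80% power in t tests", for a comparison of two independent means. It does not say which measure the 0.6 refers to. Its sidedness is not in the readable text, and Figure 1 is not shown.

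Section 11.3.3 sends the secondary variables, apart from safety, to exploratory data analysis. The readable text contains no lead measure, testing order, either/both rule, alpha split or composite of TNSS and PNIF.

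**The concern.** The plan sets two primary between-arm tests, each with its own 5% chance of a false positive, and does not say how they combine into one conclusion. Each natural reading has a cost. If a significant result on either measure is enough, the overall error exceeds the stated 5%. If both are required, error is controlled, but the sample size was worked out for one comparison.

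The practical risk is a split result, with one measure below 0.05 and the other not. Under the current text it could be called positive or negative after the data are seen. The two measures also differ in kind: TNSS is self-rated (Appendix 1) by participants who have read their own dosing instructions (section 6.5), while PNIF is an airflow measurement (section 9.6). So it matters which one carries the claim.

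**Working it through.** **Inputs from the documents.** Total 72 with equal allocation (sections 11.1 and 6.6), so 36 per arm; d=0.6; 80% power; threshold 0.05; two-sample t test.

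**Assumptions, not in the documents.** Correlation r between the two test statistics, oriented so that improvement is positive, from 0 to 0.9; d=0.6 on each measure unless stated; all 72 analysed; both one- and two-sided tests tried.

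**Step 1. Reproduce the sample size.** The noncentrality is d × √(n/2) = 0.6 × √18 = 2.546, with 70 degrees of freedom.
- One-sided 0.05 (critical value 1.667): power 80.9%. With 35 per arm it is 79.96%, so 72 is the smallest equal-arm total that reaches 80%. The plan's figure is reproduced.
- Two-sided 0.05 (critical value 1.994): power 70.9%; 80% would need 90. The plan's figure is not reproduced.

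**Step 2. Either result counts, each at 0.05.** Error = 1 − P(neither test significant when there is no effect). At r=0 this is 1 − 0.95² = 9.75%. For r above 0 it comes from the bivariate normal distribution.

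**Step 3. Both must succeed.** Joint power = Φ₂(Φ⁻¹(p), Φ⁻¹(p); r), where p is the single-test power. At r=0 this is 0.8095² = 65.5% one-sided and 0.7090² = 50.3% two-sided.

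| r | Error if either counts, 1-sided / 2-sided | Joint power at N=72, 1-sided / 2-sided | Total N for 80% joint power, 1-sided / 2-sided |
|---|---|---|---|
| 0 | 9.75% / 9.75% | 65.5% / 50.3% | 96 / 118 |
| 0.5 | 8.8% / 9.1% | 70.0% / 56.8% | 90 / 112 |
| 0.8 | 7.5% / 7.8% | 74.1% / 62.2% | 84 / 104 |
| 0.9 | 6.8% / 7.0% | 76.1% / 64.8% | 80 / 100 |

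**Step 4. Unequal effects, one-sided, N=72.** One measure is kept at d=0.6 and the other is varied.
- Other measure d=0.4: joint power 42% (r=0) to 47% (r=0.5).
- Other measure d=0.8: 77.5% (r=0) to 80.5% (r=0.8).
- Other measure d=1.0: about 80.5 to 81%.

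**Step 5. Chance of a split result when both effects are 0.6.** This is 2 × (p − joint power). One-sided: 2 × (0.809 − 0.655) = 31% at r=0, 22% at r=0.5 and 10% at r=0.9. Two-sided: 41%, 28% and 12%.

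**Step 6. Power under rules that hold 5% error.**
- Fixed sequence: the first test keeps the single-test power, 81% one-sided or 71% two-sided.
- Holm (smaller p against 0.025, then the other against 0.05): if only one measure has an effect, d=0.6, its power is about 71% one-sided or 60% two-sided. Testing at 0.025 with 80% power would need a total of 90 or 110.

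**The case against.** The strongest reply is that this is a single-centre Phase II trial with one endpoint measured in two ways, that error is bounded just under 10%, and that the repair is short. The bound and the easy repair stand. The one-endpoint argument does not: section 11.3.1 assesses each measure separately, no composite is defined, and the plan itself sets this primary comparison at p<0.05 apart from its exploratory parts.

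Four stronger readings are tempting, and the documents do not support them.
- A reader might infer that requiring both measures must bring power below 80%. That depends on the effects. Section 11.1 does not tie 0.6 to either measure. If 0.6 is the smaller effect, one-sided joint power stays near 80% when the other is about 0.8 with high correlation, or about 1.0.
- A reader might take the whole gap between 80% and the two-sided 50 to 65% as harm from the missing rule. The first part, 80% to 71%, is a sidedness matter. The readable text is silent on it, Figure 1 may settle it, and 72 matches a one-sided test.
- A reader might extend the inflation to the threshold for all tests, including secondary efficacy. Section 11.3.3 leaves those variables to exploratory analysis, so the exposure is two between-arm tests.
- A reader might add the mention of screening (V1) in the TNSS item, or the within-group changes, as further routes to success. Section 8 labels the reference visit "Visit 2 – Baseline – Day 1", and the primary objective compares the arms. These are wording points to clarify and are not counted in the error rate.

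**Conclusion.** The concern holds for the two primary between-arm tests. The direction of the error result does not depend on the assumptions: two tests at 0.05 with either sufficient exceed 5% at any correlation below 1. Its size, roughly 7 to 10%, rests on an assumed correlation of 0.9 to 0. If both are required, error is at most 5%, and joint power cannot exceed that of the weaker measure. With d=0.6 on both, it falls 5 to 15 percentage points below the single test one-sided (81% to between 76% and 65%) and 6 to 21 points two-sided (71% to between 65% and 50%). The rule should be written before unblinding, because a rule chosen after a split result would not be credible.

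**What to change.** Before unblinding, amend sections 4, 11.1 and 11.3 to state one success rule for the between-arm difference in change from D1 (V2) to D7 (V3), with sidedness.

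- **Preferred: fixed sequence.** Name the first measure and test it at 0.05; test the second at 0.05 only if the first is significant. This holds 5% error with no added participants, visits or data. The costs are that the second measure cannot succeed alone, and that the first test has 81% power if one-sided but only 71% if two-sided. The sponsor should justify the order, given that TNSS is self-rated by participants who know their instructions.
- **Alternative: Holm.** Either measure can succeed. If only one has an effect (d=0.6), its power at 72 is 71% one-sided or 60% two-sided, so the stated 80% must be revised, or the total raised to about 90 or 110.
- **If both are required.** Restate the joint power. Holding 80% needs about 80 to 96 participants one-sided (8 to 24 more) or 100 to 118 two-sided (28 to 46 more), assuming d=0.6 on both. This is not the cheap option.

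Replace the blanket 0.05 sentence in section 11.1 with a reference to the chosen rule, align section 11.3.3, and call all other p-values nominal. As minor clarifications, state that V2 is the TNSS reference and that within-group changes are descriptive. Under section 13 the amendment needs regulatory approval before it takes effect.

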11.3.2. Secondary Variables

1. Safety of the AllerPops product during a 21-day intervention period. Safety will be assessed by collecting vital signs, the emergence of adverse events, clinical chemistry (CBC and a comprehensive safety panel) and PI assessment.
2. The change of nasal symptoms will be measured based on the following variables during a 21-day intervention period:
 - The Total Nasal Symptoms Score (TNSS) score change will be assessed by comparing control group and investigational group.
 - Peak Nasal Inspiratory Flow (PNIF) values change will be assessed by comparing control group and investigational group.
3. Amplicon Metagenomics Sequencing values change during a 21-day intervention period will be assessed by comparing control group and investigational group.
4. IgE (total) blood level change during a 21-day intervention period will be assessed by comparing control group and investigational group.

11.3.3. Data Analysis

A descriptive statistics study will be performed for the primary variables. Continuous variables will be presented with the average and standard deviation or median range, as appropriate, and categorical variables will be presented as proportions. Parametric or non-parametric independent or related samples tests will be used, according to whether the distribution of the data in each variable is normal or not. A p-value < 0.05 is considered statistically significant. An EDA will be performed for the secondary variables (except safety) to analyze and investigate data sets and summarize their main characteristics, employing data visualization methods.

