9.9.1. Endpoint-Related Samples

The following endpoints will be collected for each visit during the trial life cycle:

- V1-screening: Vital signs (Body temperature, blood pressure, and heart rate) will be measured and Blood Clinical Chemistry samples will be collected. Total Nasal Symptoms Score (TNSS) will be administered. A physical examination will be completed.
- V2-Baseline (D1): Total Nasal Symptoms Score (TNSS), Peak Nasal Inspiratory Flow (PNIF) values, Saliva sample collection for Amplicon Metagenomics Sequencing test, Vital signs (Body temperature, blood pressure, and heart rate) will be measured and Blood Clinical Chemistry samples will be collected.
- V3- Follow up (D7): Total Nasal Symptoms Score (TNSS), Peak Nasal Inspiratory Flow (PNIF) values, Saliva sample collection for Amplicon Metagenomics Sequencing test, Vital signs (Body temperature, blood pressure, and heart rate) will be measured and Blood Clinical Chemistry samples will be collected.
- V4- Follow up: Total Nasal Symptoms Score (TNSS), Peak Nasal Inspiratory Flow (PNIF) values, and Vital signs (Body temperature, blood pressure, and heart rate) will be measured.
- V5- End of study (D21): Total Nasal Symptoms Score (TNSS), Peak Nasal Inspiratory Flow (PNIF) values, Saliva sample collection for Amplicon Metagenomics Sequencing test, Vital signs (Body temperature, blood pressure, and heart rate) will be measured and Blood Clinical Chemistry samples will be collected.

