11.3.4. Safety Analysis

The safety evaluation will include assessment of AEs, vital signs, clinical laboratory safety tests, and physical examination findings.

For each continuous laboratory parameter, results will be categorized as low, normal, or high based on the laboratory normal ranges, if applicable. Frequencies and percentages will be presented by

gender and BMI group for participants who had a shift to low and for participants who had a shift to high from baseline to any post-dosing assessment, if applicable.

The number and percentage of participants with normal and abnormal physical examination results will be presented for evaluations at baseline, each indicated visit and final visit, if applicable. Individual and summary clinical laboratory data will be presented in tabular form with mean, median, standard deviation, and range (minimum and maximum) as appropriate.

12. Protocol Deviations

Protocol Deviation (PD) forms must be filed for any deviation from this protocol. PDs which place participants at increased risk of harm, or affect data integrity may be considered Protocol Violations (PVs) and must be reported to the appropriate regulatory authorities no later than 2 weeks (10 business days) from the time of identification. PDs will be filed in the applicable participant chart, and in the Trial Master File upon study closeout. PDs will be filed and signed by delegated study staff and reviewed and signed by the PI. The PI will determine if the PD is reportable to the IRB based on an assessment of the participant's safety and/or the effects on the integrity of the study data.

13. Protocol Amendments

Any changes to the protocol must be tracked and documented in the form of an amendment after it has been reviewed by the appropriate regulatory bodies. The reasons for change must be documented in writing and provided to the regulatory bodies and included in the Trial Master File (TMF). These changes will be subject to regulatory approval prior to implementation. All amendments will be documented in the study report.

14. Data Collection and Storage

The PI and/or delegated site staff agree to maintain accurate CRFs and source documentation. Source documents are the originals of any documents which will be used by the site that allow verification of the existence of the participant and substantiate the integrity of the data collected during the trial.

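### The primary D1-to-D7 comparison names no baseline covariate and lets the data choose the test; a prespecified ANCOVA on D1 would fix the effect measure and usually narrow the interval

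*Combined protocol and SAP*

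**What the plan says.** Section 11.3.1 defines both primary variables as changes to D7, "for each group and the differences between groups (investigational and control) will be statistically assessed". For TNSS the reference is worded as "change from the screening (V1), baseline by comparing D1(V2) and D7(V3"), so both the screening visit and D1 appear. For PNIF the reference is D1 alone.

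Section 11.3.3 then sets the rule for choosing a test: "Parametric or non-parametric independent or related samples tests will be used, according to whether the distribution of the data in each variable is normal". It gives no normality test, no threshold and no effect measure.

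Section 11.1 sizes the trial on a two-sample comparison of means, and its wording is open-ended: "Parametric statistical techniques including, but not limited to t tests". It also allows transformation or replacement of a method at the final analysis, with the undertaking that "any changes will be documented in the clinical study report, including the rationale for use".

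No covariate, regression or ANCOVA is planned anywhere, and ANOVA appears only in the abbreviation list. The primary objective in Section 4 is comparative: "To assess the effectiveness of AllerPops on relieving nasal symptoms compared to the control group in volunteers". Section 9.9.1 shows that the data for adjustment already exist: "V2-Baseline (D1): Total Nasal Symptoms Score (TNSS), Peak Nasal Inspiratory Flow (PNIF) values".

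**The concern.** There are three linked weaknesses.

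- **The effect measure is not fixed.** A t test estimates a mean difference and a rank test a shift in ranks. Which of them becomes the primary result depends on how the outcome data look. TNSS (Appendix 1) is the sum of three 0-3 items, an integer from 0 to 9, so it cannot be exactly normal, and a normality check will often fail for reasons unrelated to treatment. Reporting a change of method afterwards is transparent, but it is not prespecification.
- **Precision may be left unused.** A test on change fixes the slope on baseline at 1. ANCOVA estimates it, and in large samples is never less precise.
- **Within-arm tests sit beside the between-arm test with no stated rank.** Both arms take the same product, so both may improve. A significant fall in one arm and not in the other could then be read as a difference between arms.

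At stake are the clarity of the primary result and the width of its confidence interval. The validity of the trial is not in question.

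**Working it through.** **Inputs from the documents.** N = 72, standardised effect 0.6, 80% power and p < 0.05 (Section 11.1); equal allocation (Section 6.6), so 36 per arm.

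**Inputs not in the readable text, so assumed.** The D1-D7 correlation ρ (0.3 to 0.8); k = D1 SD / D7 SD (0.7 to 1); 0.6 measured in SDs of change. Sidedness is not stated in the text, so both are shown.

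**1. The plan's own figure.** Two-sample noncentral t, noncentrality 0.6 × √(n/2), df = 2n − 2.
- One-sided 5%: 35 per arm gives 79.96%; 36 per arm gives 80.9%, so N = 72 is reproduced.
- Two-sided 5%: 36 per arm gives 70.9%; 45 per arm (N = 90) is needed for 80%.

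Only the one-sided reading reproduces 72, and on that reading the plan already meets its power target.

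**2. Variance ratio.** In units of the D7 variance, the change score has variance k² + 1 − 2ρk and the ANCOVA residual has variance 1 − ρ². The first minus the second is (k − ρ)², which is never negative. So

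R = (1 − ρ²) / (k² + 1 − 2ρk) ≤ 1, with equality at ρ = k.

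Estimating the slope costs one df (69 instead of 70) and a factor 1 + 1/(2n − 4) = 1 + 1/68 = 1.0147.

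**3. Worked cell, ρ = 0.5, k = 1.** R = 0.75/1 = 0.75. With the slope cost, 0.75 × 1.0147 = 0.761. The effective effect is 0.6/√0.761 = 0.688 and the noncentrality is 0.688 × √18 = 2.92. One-sided power is 89.3%, against 80.9% for the t test.

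**4. Whole grid, 36 per arm, slope cost included.**

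| k | ρ | R | One-sided power, % (t test 80.9) | 95% CI half-width, change SDs (t test 0.470) |
|---|---|---|---|---|
| 1 | 0.3 | 0.650 | 92.8 | 0.382 |
| 1 | 0.5 | 0.750 | 89.3 | 0.410 |
| 1 | 0.7 | 0.850 | 85.8 | 0.437 |
| 1 | 0.8 | 0.900 | 84.0 | 0.449 |
| 0.8 | 0.3 | 0.784 | 88.1 | 0.420 |
| 0.8 | 0.5 | 0.893 | 84.2 | 0.448 |
| 0.8 | 0.7 | 0.981 | 81.1 | 0.469 |
| 0.8 | 0.8 | 1.000 | 80.4 | 0.474 |
| 0.7 | 0.3 | 0.850 | 85.7 | 0.437 |
| 0.7 | 0.5 | 0.949 | 82.2 | 0.462 |
| 0.7 | 0.7 | 1.000 | 80.4 | 0.474 |
| 0.7 | 0.8 | 0.973 | 81.4 | 0.467 |

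The t-test half-width is 1.994 × √(2/36) = 0.470. Two-sided, the t test's 70.9% becomes about 70-87%.

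**5. Some D7 values missing.** With 32 per arm (an assumed 10% without D7 data), the one-sided t test falls to 77%. ANCOVA gives 76-90% and is at or above 80% in 6 of the 12 cells.

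**6. Data-driven test choice (simulation).** Over the same 12 cells, 4,000 trials each, run once as a continuous outcome and once as an integer 0-9 score (assumed D1 mean 6, D7 mean 4.5, D7 SD 2):
- type I error was 4.0-5.8% for the change-score t test and 4.1-5.9% for ANCOVA;
- two-sided t and Mann-Whitney verdicts differed in 5-7% of trials at an effect of 0.6, and in about 2% under the null.

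A separate simulation of an integer 0-9 score (assumed SD 1.7, means 6 and 5; ρ 0.3, 0.5, 0.7) applied a Shapiro check in each arm. It rejected normality in 44-94% of trials. The two-stage procedure kept type I error at about 4-5%.

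**7. Within-arm tests.** Suppose both arms fall equally by 0.3, 0.4 or 0.5 change SDs (assumed). The two-sided paired t test with n = 36 has power p = 0.417, 0.646 or 0.831. The chance that exactly one arm is significant is 2p(1 − p) = 0.486, 0.458 or 0.281.

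**The case against.** The planned between-arm test is valid, and on the one reading that reproduces N = 72 it has its design power. Choosing ANCOVA is then an improvement, not a repair. **This stands**, and it limits how strongly the point can be put.

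The gain rests on ρ, k and the SD behind 0.6, none of which the readable text gives. In five of the twelve cells above the one-sided gain is 1.3 points or less, and in two of those there is a loss. Telephone pre-screening selects on symptom severity (Section 8), which makes k below 1 plausible for TNSS; the same selection may also lower ρ, which works the other way. **This stands too**: no particular gain can be promised.

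Section 11.1 points to the t test as the default, and t and rank verdicts seldom disagree. That makes the harm from an open choice small, but it does not settle which effect measure will be reported.

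On within-arm tests, the objective and the sample size are both comparative, and nothing says that a within-arm result can establish efficacy. The 28-49% is therefore a caution about misreading, not about a planned inference, and one clarifying line would answer it.

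Finally, TNSS is bounded. The simulations did not test a D7 distribution with many scores near zero, which is a reason to keep a rank or permutation analysis beside the model.

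**Conclusion.** The concern holds. The plan names no baseline covariate, leaves the test to the observed distribution and so leaves the effect measure open, although the D1 values needed for a better analysis are collected anyway. The stronger part is prespecification, which does not depend on any assumed value. The precision part does. Over ρ 0.3-0.8 and k 0.7-1, with 0.6 in change SDs and 36 per arm, the 95% interval runs from 19% narrower (0.382/0.470 = 0.81) to 1% wider (0.474/0.470 = 1.01), and one-sided power from about half a point lower to 12 points higher. Nothing here suggests bias or material type I inflation. The change is recommended because it is cheap and clarifies the primary result; the planned comparison would not be invalid without it. Confidence in the size of the gain is moderate.

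**What to change.** For each primary variable, prespecify one between-arm model in Section 11.3: D7 value on arm, with the D1 (V2) value as covariate. Then:

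- report the adjusted mean difference with its 95% CI, whatever a normality check shows;
- name a rank or permutation analysis as a sensitivity analysis;
- label within-arm tests descriptive, and say that the between-arm estimate answers the primary objective;
- state V2 as the TNSS reference visit, in line with its label in Section 9.9.1, and tidy the mention of V1 in Section 11.3.1.

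Keep the significance level and sidedness as the design sets them. Sidedness and the handling of missing D7 values are separate points.

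The cost is one degree of freedom, about half a power point in the worst case (ρ = k), and a protocol amendment, for which Section 13 says: "These changes will be subject to regulatory approval prior to implementation". It needs no new data and no extra participants.
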